We propose a pilot study to treat 1) Sub-acute concussion with OXE-103 in Part A and 2) Acute concussion management with OXE-103 within 24 hours of presentation to the Trauma Unit in Part B. For Part A, we will recruit subjects from the University of Kansas Health System Center for Concussion Management (CCM) clinics which include Neurology, Sports Medicine, and Neurosurgery/PM&R. For Part B, we will recruit subjects from the University of Kansas Health System Trauma Unit. In Part A we will compare an open-label treatment arm (OXE-103) to a non-treatment concurrent control arm. Part B will be randomized double blind 1:1 to treatment with OXE-103 and placebo. We will compare these using self-report symptom scoring, quality of life questionnaires, computerized cognitive testing assessing executive function, memory and processing speed, and accelerometer-based balance scoring. The exploratory nature of this study is not powered to yield statistically significant outcomes, but will allow detection of trends within subjects and between groups, will support comparison with standard tests of neurocognitive functions, and will provide sample size estimates for future studies of people with persistent concussion related symptoms.

This study is highly relevant clinically and uniquely suited to being conducted at the CCM. It will be the first to test ghrelin as therapy for sub-acute concussion.

Specific Aims:

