In Part B the design will be randomized, double-blinded, and placebo-controlled with Arm 1 receiving OXE-103 and Arm 2 receiving placebo. The enrollment target will be 20 subjects receiving OXE-103 and 20 subjects receiving placebo. Up to 50 subjects may be enrolled in Arms 1 and 2 combined to allow for replacement of subjects who may not complete the study requirements.

In Part A Arm 1 and Part B both Arms 1 & 2, the maximum enrollment will be 80 subjects. For the Part A Arm 2 (non-treatment concurrent control) the minimum target enrollment will be 20 subjects, but there will be no maximum number.

We will randomize using the REDCap database. The database will be set up to share randomization allocation only with the statistician and Investigational Pharmacy. All subjects will be consented and either begin treatment within 24 hours of presentation to the Trauma Unit (for Part B) or ≤ 28 days post-injury (for Part A). For Part A, starting on Day 1, the treatment cohort (Arm 1) will receive OXE-103 40ug/kg twice daily by self-injection and the non-treatment control group (Arm 2) will begin their monitoring. For Part B, on Day 1 (within 24 hours of being admitted into the Trauma Unit) the treatment Arm will receive OXE-103 40ug/kg SC twice daily by self-injection and the placebo Arm will receive a placebo injection SC twice daily. OXE-103 and placebo will be maintained and dispensed by Investigational Pharmacy. Subjects will receive an 8-day supply of syringes pre-loaded with OXE-103 or placebo. Each cohort receiving OXE-103 or placebo will receive the 2nd set of syringes with OXE-103 or placebo at the Day 8 visit. Appropriate therapy that would be considered standard of care by the Principal Investigator or Co-Investigator will be administered or prescribed at any time during subjects' study participation.

Subject training

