5.1 Primary Efficacy Outcome Measures

- PCSS severity responder as defined by $\geq 20\%$ improvement over baseline at Day 15 in the severity score
- PCSS symptom responder as defined by $\geq 20\%$ improvement over baseline at Day 15 in the number of symptoms
- PCSS 4MBS responder as defined by $\geq 20\%$ improvement over baseline at Day 15 in the 4MBS severity score
- Change from baseline in PCSS severity score at each post-baseline assessment (Days 4, 8, 11, 15, 21 and 44)
- Change from baseline in PCSS number of symptoms at each post-baseline assessment (Days 4, 8, 11, 15, 21 and 44)
- Change from baseline in PCSS 4MBS severity score at each post-baseline assessment (Days 4, 8, 11, 15, 21 and 44)

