6.1 General Methods

This pilot study will describe changes observed in the two treatment groups, placebo versus OXE-103, separately for each part. Since the study is exploratory, analyses will focus on descriptive comparative statistics and not on a pre-specified statistically significant primary endpoint. Data will be used to enable power calculations and the definition of suitable clinical endpoints for further clinical development. Data from baseline and on Study Days 4, 8, 11, 15, 21, and 44 will be analyzed. Note that day definitions in this study will follow the Clinical Data Interchange Standards Consortium in that there is no Day 0;

assessments performed prior to randomization will be done on Days -7 and -3 (Part A only) and randomization is considered Day 1.

For all evaluations of changes from baseline, baseline is defined as the last reported value before the first dose of study drug. In most instances, this will be the value recorded on Day 1.

For the evaluation of safety, a treatment-emergent finding is any result that is newly reported after the first dose of study drug. This may include an existing condition which worsens in severity after the start of treatment.

Continuous variables such as total score or change from baseline will be summarized by the number of observations, mean, standard deviation, median, minimum and maximum value. Graphs of changes from baseline over time will present the means and 95% confidence intervals.

Binary or categorical variables will be summarized by the number of observations in each category along with the percent of observations.

To aid in interpretation of the importance of relationships, correlation coefficients (Pearson and Spearman) will be reported with p-values.

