6.13 Adjustment for Covariates

No statistical modeling is planned for this exploratory study, therefore, there will be no adjustment for covariates.

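### In randomised Part B the SAP rules out adjusting for the Day 1 score and gives no between-arm estimate, so the trend it promises is less precise than the data allow

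*SAP*

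**What the plan says.** The Protocol (Proposed Clinical Trial) fixes the Part B design: "Part B will be randomized double blind 1:1 to treatment with OXE-103 and placebo". Under General study design it sets the size, "The enrollment target will be 20 subjects receiving OXE-103 and 20 subjects receiving placebo", with a ceiling: "Up to 50 subjects may be enrolled in Arms 1 and 2 combined". On allocation it says "We will randomize using the REDCap database", and it describes no stratification by Day 1 score.

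The Part B schedule of events collects PCSS, QOLIBRI, PGAS and BrainCheck on Day 1. SAP 6.1 sets the reference point: "baseline is defined as the last reported value before the first dose of study drug", usually Day 1.

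SAP 5.1 defines the continuous primary measures as raw change, for example "Change from baseline in PCSS severity score at each post-baseline assessment (Days 4, 8, 11, 15, 21 and 44". The symptom count, 4MBS, QOLIBRI, PGAS and BrainCheck measures in SAP 5.1 and 5.2 take the same form. SAP 6.8 summarises values and changes for each group and visit, and plots the arm means with 95% intervals. It specifies no difference between arms.

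SAP 6.13 closes off any other use of the Day 1 score: "No statistical modeling is planned for this exploratory study, therefore, there will be no adjustment for covariates". SAP section 1 says the SAP prevails over the protocol on analyses, so the protocol does not supply the adjustment.

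**The concern.** The SAP uses the Day 1 value only by subtracting it, which fixes its coefficient at 1. When the slope of Day 15 on Day 1 is below 1, subtraction over-corrects: the arm that starts higher by chance appears to improve more. With about 20 per arm and no described stratification, nothing in the design keeps the Day 1 gap small.

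This matters because Part B is the only randomised, blinded comparison in the study. SAP section 4 says the pilot will allow trends between groups to be seen, and SAP 6.1 adds: "Data will be used to enable power calculations and the definition of suitable clinical endpoints for further clinical development". A reader has to form the Part B contrast from two arm means, and that contrast is noisier than the collected data require.

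The point is limited to precision in Part B. Part A is non-randomised under the current protocol, which raises a different problem (confounding).

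**Working it through.** **Inputs.** n = 20 per arm (Protocol, General study design), with 25 per arm as a check because the Part B ceiling is 50. Two-sided 95% intervals, matching the SAP graphs. The documents give no SD and no Day 1 to Day 15 correlation ρ. Results are therefore in SD units, with ρ varied and, at first, equal SDs on Day 1 and Day 15. These are assumptions.

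**The plan's own figure.** There is no power or sample-size calculation to reproduce. The only arithmetic available is the enrolment maximum, 30 (Part A Arm 1) + 50 (Part B) = 80, which agrees with the protocol.

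**Step 1: chance imbalance.** The SE of the difference in Day 1 means is √(2/20) = 0.316 SD. The chance of a gap above 0.5 SD is P(|Z| > 0.5/0.316 = 1.58) = 0.114, or about 11%.

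**Step 2: effect on the raw-change contrast.** Given a Day 1 gap, the raw-change difference moves by −(1 − slope) × gap, where slope = ρ × SD15/SD1 (equal to ρ under equal SDs). At ρ = 0.5:
- a gap of one SE moves it by 0.5 × 0.316 = 0.16 SD;
- a gap of 0.5 SD moves it by 0.25 SD.

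In 20,000 simulated trials at each ρ, the raw-change difference correlated −0.59, −0.50 and −0.38 with the Day 1 gap at ρ = 0.3, 0.5 and 0.7. The ANCOVA difference correlated about 0. Both averaged to essentially no error over randomisations.

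**Step 3: precision under equal SDs.**
- Raw change: variance of the arm difference = 2(1 − ρ) × 2/n; t with 38 df.
- ANCOVA: variance = (1 − ρ²) × (2/n) × (1 + 1/36); t with 37 df. The last factor is the cost of estimating the slope.
- Large-sample variance ratio: (1 − ρ²)/[2(1 − ρ)] = (1 + ρ)/2.

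| ρ | Half-width, raw change (SD) | Half-width, ANCOVA (SD) | Narrower by |
|---|---|---|---|
| 0.3 | 0.757 | 0.620 | 18% |
| 0.5 | 0.640 | 0.563 | 12% |
| 0.7 | 0.496 | 0.464 | 6% |
| 0.8 | 0.405 | 0.390 | 4% |
| 0.9 | 0.286 | 0.283 | 1% |

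Worked row, ρ = 0.5: raw change √(1.0 × 0.1) = 0.316, × 2.024 = 0.640; ANCOVA √(0.75 × 0.1 × 1.028) = 0.278, × 2.026 = 0.563; ratio 0.879. The gain is cancelled at ρ of about 0.94. The simulation gave mean half-width ratios of 0.818, 0.879 and 0.935 at ρ = 0.3, 0.5 and 0.7. At 25 per arm and ρ = 0.5 the half-widths are 0.569 and 0.498, again about 12% narrower.

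**Step 4: unequal SDs.** Var(change) − Var(ANCOVA) is proportional to (SD1 − ρ·SD15)², which is never negative. With the Day 15 SD from 0.6 to 1.5 times the Day 1 SD and ρ from 0.2 to 0.8, the large-sample variance ratio ran from 0.31 to 1.00. The gain can thus be much larger than in the table, or nil, but adjustment is not worse in large samples.

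**The case against.** **The study is exploratory and not powered.** Simple summaries in a 20-per-arm pilot with bounded scores are a defensible choice, the SAP states it openly, and no decision rule in the documents is broken. That stands, and it limits this to a recommended improvement. It does not settle the matter: the same SAP promises between-group trends and planning inputs, and already plans correlation p-values (SAP 6.1, 6.8) and an ROC search for the cut-off that best separates the arms (SAP 6.8). An adjusted difference with an interval is no more confirmatory than these.

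**The between-arm interval is not a planned quantity.** This is correct. The percentages describe the contrast that a reader or planner would form. A reader might go on to infer a loss of power, but SAP section 4 disclaims any powered test, so there is no stated power to lose.

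**Equal SDs may be wrong.** This stands as a limit on the size. In a simulated example with PCSS severity cut at 20 (assumed mean 35, SD 18, untruncated ρ = 0.5), the SDs became 13.7 and 17.0 with ρ = 0.40. The variance ratio was then 0.84, not the 0.70 that (1 + ρ)/2 gives, and the interval was about 7% narrower rather than about 15%. Recovery could shrink the Day 15 SD and push the other way.

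**Stronger readings that the documents do not support.**
- A reader might infer that the entry floor of 20 drives the slope below 1. Under a linear relation, selecting on the Day 1 score leaves the slope unchanged: it stayed at 0.30, 0.50 and 0.70 after truncation in simulation. The slope is below 1 whenever ρ < SD1/SD15, with or without a floor, and the floor applies only to PCSS severity.
- A reader might infer that the planned tables give a later trial the wrong variance input. SAP 6.8 tabulates values as well as changes, and SAP 6.1 includes their SDs. For the same subjects the covariance is (V1 + V15 − Vchange)/2, from which the correlation and residual SD follow. Missing Day 15 values make this approximate, but the information is there.

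**Conclusion.** The point holds as one of precision and conditional error in Part B. Leaving out the Day 1 score widens the arm comparison a reader can form by an amount that depends on an undocumented correlation: under equal SDs the adjusted interval is about 18%, 12% and 6% narrower at ρ = 0.3, 0.5 and 0.7, and the gain is negligible above about 0.9. The raw contrast also moves with a chance Day 1 gap whose SE is 0.32 SD.

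A reader might infer that the planned Part B analysis is biased. It is not: with 1:1 randomisation, raw change is unbiased over repeated allocations, and the error arises only given the imbalance that happens to occur. Strictly, that property belongs to the full randomised set. SAP 6.2 uses a per-protocol set for efficacy, and baseline adjustment does not repair that choice. Nor does it touch the three responder measures listed first in SAP 5.1.

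**What to change.** In SAP 6.8 and 6.13, for Part B only, add one ANCOVA per continuous outcome (PCSS severity, number of symptoms, 4MBS, QOLIBRI total, PGAS, BrainCheck composite): Day 15 value on arm and the subject's own Day 1 value. Report the baseline-adjusted between-arm difference with its 95% interval beside the planned raw summaries, labelled descriptive and with no significance claim. Print the residual SD and the Day 1 to Day 15 correlation as well. They can be recovered from the planned SDs, but stating them directly is more convenient for planning.

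The cost is a paragraph in the SAP and one short procedure per outcome, on data already scheduled. The statistical price is one degree of freedom and an assumed linear slope on bounded scores; keeping the raw summaries alongside lets readers judge that assumption. The November 2020 SAP needs revising in any case, because it still describes a randomised Part A with a screening week. SAP 6.14 places unblinding after database lock for each part. If the change is made before then, the adjusted analysis is prespecified. If it is made later, SAP section 1 requires it to be documented as a deviation, with its timing relative to unblinding.

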6.14 Interim Analyses

There are no plans for any unblinded interim analyses. Unblinding will occur after the last subject has completed or discontinued from each part of the study, and the study database for that part has been cleaned and locked.

It is anticipated that blinded data review will occur during to study in order to ensure that assumptions which served as the basis for planned analyses are appropriate.

